7.1 Safety Follow-up Evaluations

A safety follow-up visit should occur when subjects permanently stop study treatment for whatever reason (toxicity, progression, or at discretion of site investigator) and should be performed 30 days (+7 days) after the last dose of treatment or before the initiation of a new anticancer treatment, whichever comes first. Subjects who have an ongoing \geq grade 2 or serious AE (SAE) at this visit will continue to be followed until the AE resolves to \leq Grade 1 or baseline, is deemed clinically insignificant, and/or until a new anti-cancer treatment starts, whichever is earlier.

7.2 Long Term Follow-up Evaluations

Subjects without documented disease progression will be followed for disease progression every 3 months for 1 year from day 30 visit. Once disease progression is documented, subjects will enter a survival follow up period every 3 months from the time of documented progression until death or lost to follow up. This follow up may be accomplished via phone call, email, telehealth, or communication with a local physician.

8. BIOSPECIMEN STUDIES AND PROCEDURES

8.1 **Prior Genetic Sequencing Results**

If prior genetic sequencing results were performed as per standard of care, they will be submitted at C1D1. If prior genetic sequencing was not performed, it should be ordered as standard of care. In this case, a subject may be enrolled, and genetic sequencing results will be submitted when available. If a subject does not have archival tissue available, a new biopsy is recommended but is not mandatory. In particular, markers such as BRCA1, BRAC2, TP53, CDKN2A, and KRAS will be noted in the database. Results of tumor molecular profiling may be used for correlation with tumor response to treatment.

8.2 Tissue from Surgical Resection

For subjects that undergo surgical resection, a sample of this tissue is required. This sample may be analyzed for molecular profiling including expression of biomarkers and somatic mutations by next-generation sequencing. Results of tumor molecular profiling may be used for correlation with tumor response to treatment.

8.3 Peripheral Blood

Peripheral blood collection will occur prior to treatment on cycle 1, day 1, then after every 2 cycles of FOLFOX-nal-IRI (that is, every 4 weeks) and at the safety follow up visit. Plasma will be processed from the peripheral blood for future metabolite profiling and circulating tumor DNA analysis.

8.4 Central Image Analysis

Central image analysis on coded images will be performed at the end of the study to analyze inter-institutional variability of the overall resectability rate. All CT/MRI images obtained throughout the study will be submitted at the end of study. See Imaging Manual for image labeling and shipping/transfer instructions.

8.5 Banking of Leftover Biospecimens

Subject consent will be obtained to bank any leftover samples collected for study-specific correlative research. Hoosier Cancer Research Network (HCRN), as Administrative Headquarters for the Big Ten CRC, will manage the banked samples. Samples will be banked indefinitely in the Hoosier Cancer Research Network Biorepository and used for future unspecified cancer-related research.

8.5 Banking Samples for Future Unspecified Research

Subject consent will be obtained to collect additional samples and store coded images for future unspecified Big Ten Cancer Research Consortium studies. HCRN will manage the banked samples. Samples will be banked indefinitely in the HCRN Biorepository. This includes:

- Whole blood: Whole blood will be collected prior to treatment on Cycle 1 Day 1.
- Pre- and Post-treatment plasma: Whole blood for plasma will be collected prior to treatment on Cycle 1 Day 1 and at the 30-day Safety Follow-up visit.
- Pre- and Post-treatment serum: Whole blood for serum will be collected prior to treatment on Cycle 1 Day 1 and at the 30-day Safety Follow-up visit.
- Central image analysis and storage of coded images. These images will be stored centrally at Penn State for future use after the planned analysis for this trial.

Please refer to the Correlative Laboratory Manual (CLM) and Imaging Manual for all sample collection, processing, labeling, and shipping instructions.

8.6 Confidentiality of Biospecimens

Samples will be identified by a subject's study number assigned at the time of registration to the trial. Any material issued to collaborating researchers will be anonymized and only identified by the subject's study number.

9. CRITERIA FOR DISEASE EVALUATION

9.1 Measurable Disease

Measurable disease is defined as the presence of at least one measurable lesion. Measurable lesions are defined as those that can be accurately measured in at least one dimension (longest diameter to be recorded) as ≥ 20 mm by chest x-ray, as ≥ 10 mm with CT scan, or ≥ 10 mm with calipers by clinical exam. All tumor measurements must be recorded in millimeters (or decimal fractions of centimeters).

9.1.1 Malignant Lymph Nodes

To be considered pathologically enlarged and measurable, a lymph node must be ≥ 15 mm in short axis when assessed by CT scan (CT scan slice thickness recommended to be no greater than 5 mm). At baseline and in follow-up, only the short axis will be measured and followed.

9.2 Non-measurable Lesions

All other lesions (or sites of disease), including small lesions (longest diameter <10 mm or pathological lymph nodes with ≥ 10 to <15 mm short axis), are considered non-measurable

disease. Bone lesions, leptomeningeal disease, ascites, pleural/pericardial effusions, lymphangitis cutis/pneumonitis, inflammatory breast disease, and abdominal masses (not followed by CT or MRI), are considered as non-measurable.

NOTE: Cystic lesions that meet the criteria for radiographically defined simple cysts should not be considered as malignant lesions (neither measurable nor non-measurable) since they are, by definition, simple cysts. 'Cystic lesions' thought to represent cystic metastases can be considered as measurable lesions, if they meet the definition of measurability described above. However, if non-cystic lesions are present in the same subject, these are preferred for selection as target lesions.

9.3 Target Lesions

All measurable lesions up to a maximum of 2 lesions per organ and 5 lesions in total, representative of all involved organs, should be identified as target lesions and recorded and measured at baseline. Target lesions should be selected on the basis of their size (lesions with the longest diameter), be representative of all involved organs, but in addition should be those that lend themselves to reproducible repeated measurements. It may be the case that, on occasion, the largest lesion does not lend itself to reproducible measurement in which circumstance the next largest lesion which can be measured reproducibly should be selected. A sum of the diameters (longest for non-nodal lesions, short axis for nodal lesions) for all target lesions will be calculated and reported as the baseline sum diameters. If lymph nodes are to be included in the sum, then only the short axis is added into the sum. The baseline sum diameters will be used as reference to further characterize any objective tumor regression in the measurable dimension of the disease.

9.4 Non-target Lesions

All other lesions (or sites of disease) including any measurable lesions over and above the 5 target lesions should be identified as non-target lesions and should also be recorded at baseline. Measurements of these lesions are not required, but the presence, absence, or in rare cases unequivocal progression of each should be noted throughout follow-up.

9.5 Evaluation of Target Lesions

NOTE: In addition to the information below, also see section 4.3.2 in the international criteria proposed by the Response Evaluation Criteria in Solid Tumors (RECIST) Committee, version 1.1 (Eur J Cancer 45;2009:228-247) for special notes on the assessment of target lesions.

Complete	Disappearance of all target lesions. Any pathological lymph
Response (CR)	nodes (whether target or non-target) must have reduction in
	short axis to <10 mm.
Partial Response	At least a 30% decrease in the sum of the diameters of target
(PR)	lesions, taking as reference the baseline sum diameters
Progressive	At least a 20% increase in the sum of the diameters of target
Disease (PD)	lesions, taking as reference the smallest sum on study (this
	includes the baseline sum if that is the smallest on study). In
	addition to the relative increase of 20%, the sum must also
	demonstrate an absolute increase of at least 5 mm. (Note: the

	appearance of one or more new lesions is also considered progressions).
Stable Disease	Neither sufficient shrinkage to qualify for PR nor sufficient
(SD)	increase to qualify for PD, taking as reference the smallest sum
	diameters while on study

9.6 Evaluation of Non-target Lesions

Complete Response (CR)	Disappearance of all non-target lesions and normalization of tumor marker level. All lymph nodes must be non-pathological in size (<10 mm short axis)	
	Note: If tumor markers are initially above the upper normal limit, they must normalize for a subject to be considered in complete clinical response.	
Non-CR/ Non-PD	Persistence of one or more non-target lesion(s) and/or maintenance of tumor marker level above the normal limits	
Progressive Disease (PD)	Appearance of one or more new lesions and/or unequivocal progression of existing non-target lesions. Unequivocal progression should not normally trump target lesion status. It must be representative of overall disease status change, not a single lesion increase.	

Although a clear progression of "non-target" lesions only is exceptional, the opinion of the site investigator should prevail in such circumstances, and the progression status should be confirmed at a later time by the sponsor investigator.

9.7 Evaluation of Overall Response

Target Lesions	Non-Target Lesions	New Lesions	Overall Response	
CR	CR	No	CR	
CR	Non-CR/ Non-PD	No	PR	
CR	Not evaluated	No	PR	
PR	Non-PD/ or not all evaluated	No	PR	
SD	Non-PD or not all evaluated	No	SD	
Not all evaluated	Non-PD	No	Non-evaluable	
PD	Any	Yes or No	PD	
Any	PD*	Yes or No	PD	
Any	Any	Yes	PD	
*In exceptional circumstances, unequivocal progression in non-target lesions may be accepted as disease progression.				

Subjects with a global deterioration of health status requiring discontinuation of treatment without objective evidence of disease progression at that time should be classified as having "symptomatic deterioration". Every effort should be made to document the objective progression even after discontinuation of treatment.

In some circumstances, it may be difficult to distinguish residual disease from normal tissue. When the evaluation of complete response depends on this determination, it is recommended that the residual lesion be investigated (fine needle aspirate/biopsy) to confirm the complete response status.

9.8 Definitions for Response Evaluation – RECIST 1.1

9.8.1 First Documentation of Response

The time between initiation of therapy and first documentation of PR or CR.

9.8.2 Confirmation of Response

To be assigned a status of complete or partial response, changes in tumor measurements must be confirmed by repeat assessments performed no less than four weeks after the criteria for response are first met.

9.8.3 Objective Response Rate

The objective response rate is the proportion of all subjects with confirmed PR or CR according to RECIST 1.1, from the start of treatment until disease progression/recurrence (taking as reference for progressive disease the smallest measurements recorded since the start of treatment).

9.8.4 Disease Control Rate

The disease control rate is the proportion of all subjects with stable disease (SD) for 8 weeks, or partial response (PR), or complete response (CR) according to RECIST 1.1, from the start of treatment until disease progression/recurrence (taking as reference for progressive disease the smallest measurements recorded since the start of treatment).

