OBJECTIVES	Primary Objective:Determine the disease control rate (DCR) of liposomal irinotecan (nal-IRI) in combination with oxaliplatin, leucovorin, and 5-fluorouracil(FOLFOX) for treatment of locally advanced pancreatic carcinoma.
	 Secondary Objectives: Describe the objective response rate (ORR) at 8 weeks, 16 weeks, and 24 weeks following starting FOLFOX-nal-IRI. Describe the stable disease rate (SDR) at 8 weeks, 16 weeks, and 24 weeks following starting FOLFOX-nal-IRI. Describe the proportion of subjects able to undergo surgical resection of tumor. Describe the response of serum CA 19-9 after every 2 cycles (every 4 weeks) following starting FOLFOX-nal-IRI. Determine progression-free survival (PFS). Determine overall survival (OS). Describe the quality of life after every 4 cycles (every 8 weeks) following starting FOLFOX-nal-IRI.
	 Exploratory Objectives: Determine FOLFOX-nal-IRI induced DNA damage/repair and apoptosis in biopsied and surgically resected tumor tissues. Determine DNA damage in blood-based biopsies prior to treatment and following every 4 cycles (8 weeks) of treatment. Determine the tumor molecular profile prior to initiation of chemotherapy and correlate with treatment responses. Determine the metabolic profiles of plasma prior to treatment and following every 4 cycles (8 weeks) of treatment. Examine the inter-institutional variability of the overall resectability rate.
STUDY DESIGN	This is a phase II, single-arm, open-label, clinical study to investigate the efficacy and tolerability of a combination of liposomal irinotecan (nal-IRI) with oxaliplatin, leucovorin, and 5-fluorouracil (FOLFOX-nal-IRI) for treatment of patients with locally advanced pancreatic carcinoma (LAPC). Each subject will be screened for eligibility by evaluation including medical history, physical examination, performance status, blood tests, computed tomographic (CT) scans, and electrocardiogram. Within 28

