2.1.1 Primary Objective

Estimate the disease control rate (DCR) at 24 weeks for nal-IRI in combination with oxaliplatin, leucovorin, and 5-fluorouracil (FOLFOX-nal-IRI), in subjects with locally advanced pancreatic carcinoma (for the subjects whose tumors remain unresectable following 12 cycles of FOLFOX-nal-IRI).

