2.2 Endpoints

2.2.1 Primary Endpoint

Disease control rate (DCR) as determined by the proportion of subjects with complete response, partial response, or stable disease, as defined by RECIST 1.1, at 24 weeks following initiation of FOLFOX-nal-IRI (for the subjects whose tumors remain unresectable following 12 cycles of FOLFOX-nal-IRI).

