12.2 Endpoints

12.2.1 Definition of Primary Endpoint

Disease control rate (DCR) as determined by the proportion of subjects with complete response, partial response, or stable disease, at 24 weeks following initiation of FOLFOX-nal-IRI.

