12.3 Sample Size and Accrual

It is assumed that LAPC patients have a DCR of 45% with standard of care, whereas LAPC patients will have DCR rate of 75% under the protocol in this study. A minimax Simon's two-stage design will be implemented with 12 patients evaluated in the first stage. If 5 or fewer responses are observed from these 12 patients, then the study will be stopped for futility. Otherwise, an additional 13 patients will be added yielding a total sample size of 25 patients. The study will be considered successful if 16 or more responses are observed in the 25 patients. This design comprises a type 1 error rate of 5% and a power of 80% when the true DCR is 75%.

Therefore, this study seeks to recruit 12 to 25 patients depending on results of the first stage evaluation. Assuming approximately 10% of the patients would not be evaluable, the target sample size is 28 patients.

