12.5 Assessment of Efficacy

This will comprise all subjects who receive at least one dose of trial drug and either undergo at least one post-baseline assessment or die before any evaluation.

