12.7 Interim Analysis/Criteria for Stopping Study

A single interim analysis for futility will take place when the 12th subject has completed 6 months of follow-up. The proportion of subjects that is tumor progression-free at 6 months will be assessed along with other efficacy and safety data in making the determination if the study should continue. If 5 or fewer responses are observed from these 12 patients, then the study will be stopped for futility. Otherwise, an additional 13 patients will be added yielding a total sample size of 25 patients. Accrual will continue during the interim analysis. Recruitment will be halted if futility is determined.

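### Section 9.8.4 defines disease control by 8 weeks of stable disease, which contradicts the primary endpoint of CR, PR or SD at 24 weeks

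*Combined protocol and SAP*

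**What the plan says.** **Definition in the response criteria.** Section 9.8.4, in the list of RECIST definitions, counts "stable disease (SD) for 8 weeks, or partial response (PR), or complete response (CR) according to RECIST 1.1, from the start of treatment" until progression or recurrence. Its denominator is all subjects.

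**Primary endpoint.** Section 2.1.1 reads "Estimate the disease control rate (DCR) at 24 weeks for nal-IRI in combination". Section 2.2.1 counts CR, PR or SD "at 24 weeks following initiation of FOLFOX-nal-IRI (for the subjects whose tumors remain unresectable following 12 cycles of FOLFOX-nal-IRI". Section 12.2.1 counts complete response, "partial response, or stable disease, at 24 weeks following initiation of FOLFOX-nal-IRI", and has no clause on resectability. The synopsis objective is to determine "the disease control rate (DCR) of liposomal irinotecan (nal-IRI) in combination with oxaliplatin, leucovorin" and 5-fluorouracil, with no time point.

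**Decision rules.** Section 12.3 sets a null rate of 45% and a target of 75%. The trial stops if 5 or fewer of 12 respond; "The study will be considered successful if 16 or more responses are observed in the 25 patients". For the interim, Section 12.7 waits for 6 months of follow-up on the 12th subject and says "The proportion of subjects that is tumor progression-free at 6 months will be assessed".

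**Other relevant text.** The efficacy set in Section 12.5 is "all subjects who receive at least one dose of trial drug and either undergo at least one post-baseline assessment or die before any evaluation". The secondary endpoints (2.2.2 and 12.2.2) include ORR and SDR at 8, 16 and 24 weeks, but not DCR. Footnote 7 of the study calendar places tumour assessment every 8 weeks.

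**The concern.** The trial turns on a count of subjects with disease control, and the protocol has two rules for deciding who is counted. They differ for anyone whose disease is controlled at first but progresses before week 24. Nothing in the text says which rule prevails, and 9.8.4 cannot be set aside as belonging to a secondary endpoint, because none is a disease control rate. Both the futility decision and the success decision rest on this count. The trial is open-label and single-arm, so the rule should be fixed in the text and not chosen once outcomes are visible.

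**Working it through.** **1. Scoring by pattern.** Scans fall at weeks 8, 16 and 24.

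| Course | Section 9.8.4 | Section 12.2.1 |
|---|---|---|
| SD or better at weeks 8, 16 and 24 | controlled | controlled |
| SD at week 8, progression at week 16 | controlled | not controlled |
| Confirmed PR, progression before week 24 | controlled | not controlled |
| Progression at week 8 | not controlled | not controlled |

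The two definitions part company in one direction only: 9.8.4 can add subjects to the 24-week count.

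**2. Effect at the boundary.** One subject of the second or third kind changes 15 of 25 (failure) to 16 of 25 (success), or 5 of 12 (stop) to 6 of 12 (continue). This step needs no assumption about rates.

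**3. The plan's own figures.** Inputs from Section 12.3: first stage 12, continue with 6 or more; total 25, success with 16 or more. For a true rate p,

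P(success) = sum over x = 6 to 12 of C(12, x) p^x (1 − p)^(12 − x) × P(Bin(13, p) ≥ 16 − x)

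P(futility stop) = P(Bin(12, p) ≤ 5)

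At p = 0.45 the success probability is 0.0429, within the stated 5%. At p = 0.75 it is 0.9245, not the stated 80%. That mismatch is a separate matter and nothing here depends on it; 92.5% is used below because it is what these boundaries deliver.

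**4. If 45% is the 24-week null rate but subjects are scored by 9.8.4.** The documents do not link 8-week to 24-week control, so gaps of 5, 10 and 20 points are assumed.

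| Gap | Rate scored under 9.8.4 | P(success) | P(futility stop) |
|---|---|---|---|
| 0 | 0.45 | 4.3% | 52.7% |
| 5 | 0.50 | 11.2% | 38.7% |
| 10 | 0.55 | 23.8% | 26.1% |
| 20 | 0.65 | 62.3% | 8.5% |

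**5. If 75% is an 8-week type of rate but subjects are scored at 24 weeks.** The same gaps now lie below 75%.

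| Gap | Rate scored at 24 weeks | P(success) | P(futility stop) |
|---|---|---|---|
| 0 | 0.75 | 92.5% | 1.4% |
| 5 | 0.70 | 80.4% | 3.9% |
| 10 | 0.65 | 62.3% | 8.5% |
| 20 | 0.55 | 23.8% | 26.1% |

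Section 12.6.1 quotes historical rates of 40% (gemcitabine alone) and 75% (modified FOLFIRINOX) without a time point, so the documents do not show which table is nearer the truth. Both ignore resected subjects.

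**6. The separate denominator question.** Sections 2.1.1 and 2.2.1 restrict the endpoint to subjects still unresectable after 12 cycles; 12.2.1 and 12.5 do not. Under Section 5, a subject who goes to surgery leaves study treatment and enters survival follow-up, and no text scores that subject at week 24. With assumed counts, let 4 of 25 be resected early and 14 of the other 25 − 4 = 21 be controlled. The result is 14 of 25 (failure) if resected subjects count as failures, 14 + 4 = 18 of 25 (success) if they count as controlled, and 14 of 21 if they are excluded. The 16-of-25 rule does not directly apply to the last.

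**The case against.** The strongest reply is that the primary endpoint is already fixed. Three passages labelled primary agree on 24 weeks, one of them the definition in the statistics section, and the interim waits for 6 months. Section 9.8 is a general list; its ORR entry likewise omits the 8-, 16- and 24-week points that govern ORR elsewhere. This largely stands. A reader might infer that the trial has no defined time point for its primary endpoint, but the documents do not support that. What remains is a passage headed Disease Control Rate that gives a different answer and has no other use.

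Eight weeks of SD can also be read as a minimum duration, which anyone stable at week 24 meets. That softens the conflict without removing it, because a subject who progresses at week 16 meets the minimum too.

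A reader might also think the undefined word *responses* leaves the Simon rules open to a CR/PR count, since Section 9.8 reserves response status for confirmed CR or PR. Section 12.3 frames the rule by DCRs of 45% and 75%, which ties the word to disease control. At the 18.8% ORR cited for modified FOLFIRINOX, a CR/PR count would stop the trial at stage one with probability 98.6%. This is a wording correction, not a rival reading of the test.

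Lastly, it is tempting to conclude that the type 1 error is inflated. The documents do not support that either: inflation requires both scoring by 9.8.4 and a 45% that is a 24-week rate. In the other case the loss is power.

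**Conclusion.** The contradiction is real, and 9.8.4 is wrong as written for the only endpoint it could serve. It should be fixed; it does not leave the primary endpoint undefined, because the weight of the text favours 24 weeks.

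That one subject can reverse either decision at the boundary follows from the text alone. The probabilities are illustrations. They are exact for the stated boundaries but rest on assumed gaps and, in each direction, on an assumed time point for the planning rates. They show that the choice of definition can matter a great deal, not how likely mis-scoring is.

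The conflict over who is counted is also real, but secondary and independent: it would survive the correction of 9.8.4.

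**What to change.** 1. Make Section 9.8.4 match the 24-week primary definition, or label its 8-week version descriptive with no role in the decision rules. Add the 24-week time point to the synopsis objective.
2. In the synopsis, 12.3 and 12.7, replace *responses* with subjects with disease control (CR, PR or SD) at 24 weeks, and describe the interim proportion in the same words.

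These two are wording changes, with no new visits, data or subjects. They settle how subjects are scored. They do not establish that 45% and 75% are 24-week rates, which the documents leave open.

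3. As a separate item, reconcile 2.1.1, 2.2.1, 12.2.1 and 12.5 to one denominator that matches the 16-of-25 rule, with one prespecified score for subjects resected before week 24. This is a substantive choice. Excluding resected subjects would leave fewer than the 25 the rule needs unless they are replaced. The target of 28 leaves 28 − 25 = 3 spare places, already allotted to non-evaluable subjects, so exclusion could mean more enrolment or a revised rule.
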